7.2.5 Sponsor Responsibility for Reporting Adverse Events

All Adverse Events will be reported to regulatory authorities, IRB/IECs and investigators in accordance with all applicable global laws and regulations, i.e., per ICH Topic E6 (R1) Guidelines for Good Clinical Practice.

8.0 STATISTICAL ANALYSIS PLAN

This section outlines the statistical analysis strategy and procedures for the study. Changes to analyses made after the protocol has been finalized, but prior to final database lock, will be documented in a supplemental statistical analysis plan (sSAP) and referenced in the Clinical Study Report (CSR) for the study. Post hoc exploratory analyses will be clearly identified in the CSR.

8.1 Statistical Analysis Plan Summary

Key elements of the statistical analysis plan (SAP) are summarized below; the comprehensive plan is provided in Sections 8.2 through 8.12.

Study Design Overview	This is a Phase 2, nonrandomized, multi-site, open-label trial to study the efficacy and safety of the combination regimen of MK-3682 + RZR in subjects with chronic HCV GT1, GT2, GT3, GT4, GT5, or GT6 infection. All subjects will receive MK-3682 450 mg + RZR 180 mg for 12 weeks. Subjects can be treatment-naïve or treatment-experienced with a prior IFN-based therapy, cirrhotic or non-cirrhotic, and mono-infected with HCV or co-infected with HIV. Approximately 250 subjects will be assigned to receive treatment, with target allocation based on GT (GT1, GT2, GT3, GT4, GT5, or GT6). All subjects will be followed for 24 weeks after the end of study therapy.
Treatment Assignment	All subjects will receive MK-3682 + RZR for 12 weeks.
Analysis Populations	Efficacy: Full Analysis Set (FAS), Per Protocol (PP), and modified Full Analysis Set (mFAS). Safety: All Subjects as Treated (ASaT)
Primary Endpoint(s)	Proportion of subjects achieving SVR ₁₂
Key Secondary Endpoints	Proportion of subjects achieving SVR ₂₄ ; Proportion of subjects experiencing virologic failure at FW12 among all subjects who do not discontinue study for non-treatment-related reasons.
Statistical Methods for Key Efficacy Analyses	For the primary efficacy analysis based on the FAS population, the proportions of subjects achieving SVR ₁₂ will be estimated in each GT, and 95% confidence intervals (CIs) for these rates will be calculated using the Clopper-Pearson method [42]. The missing data approach of Missing=Failure (M=F) will be utilized for the primary analysis. The same Clopper-Pearson method will be used to analyze all binary endpoints based on the mFAS population and for the PP population for each GT, and Treatment-Related Discontinuation=Failure (TRD=F) will be used as the missing data approach for both analysis populations.


Statistical Methods for Key Safety Analyses
	
The ASaT population will be used for safety analyses. The proportion of subjects with AEs of elevated laboratory values that are reported as ECIs (as described in Section 7.2.3.2) during the study therapy period will be provided along with the corresponding 95% CIs.
 
In addition, the broad clinical and laboratory AE categories consisting of the percentage of subjects with any AE, a drug-related AE, an SAE, an AE which is both drug-related and serious, and who discontinued due to an AE will be summarized in the same manner.

Interim Analyses
	
An assessment of safety for the first 50 subjects will be made. (See Section 5.11.1 for the criteria for assessing safety in the first 50 subjects.) In addition, an assessment for efficacy will be made for the first 10 per-protocol subjects enrolled in each GT, and on an ongoing basis to determine whether there is a need to modify the treatment regimen. (See Section 5.11.4 for the criteria for assessing efficacy and the initiation of treatment modifications). Finally, throughout the course of this open-label study, efficacy and safety will be monitored for trends and programmatic decisions.

Multiplicity
	
No multiplicity adjustment is planned for the study.

Sample Size and Power
	
Approximately 250 subjects will be allocated to treatment, with 35 GT1a-, 15 GT1b-, 50 GT2-, 50 GT3-, 50 GT4-, 25 GT5- and 25 GT6-infected subjects.
 
If the SVR₁₂ rate is approximately 97.1% for GT1a (34 successes out of 35), the exact 95% CI is (85.1, 99.9). If the SVR₁₂ rate is approximately 93.3% for GT1b (14 successes out of 15), the exact 95% CI is (68.1, 99.8).
 
For GT2, GT3, and GT4 where 50 subjects are targeted for treatment allocation, if the SVR₁₂ rate is 98% (49 successes out of 50), the exact 95% CI is (89.4, 99.9). If the SVR₁₂ rate is 94% (47 successes out of 50), the exact 95% CI is (83.5, 98.7).
 
For GT5 and GT6 where 25 subjects are targeted for treatment allocation, if the SVR₁₂ rate is 96% (24 successes out of 25), the exact 95% CI is (79.6, 99.9). If the SVR₁₂ rate is 92% (23 successes out of 25), the exact 95% CI is (74.0, 99.0).
 
Detailed information for varying SVR rates is in Section 8.9.1.

8.2 Responsibility for Analyses/In-House Blinding

The statistical analysis of the data obtained from this study will be the responsibility of the Clinical Biostatistics department of the Sponsor.

This trial is being conducted as an open-label study, i.e., subjects, investigators, and Sponsor personnel will be aware of subject treatment assignments after each subject is enrolled and treatment is assigned.

8.3 Hypotheses/Estimation

Objectives of the study are stated in Section 3.0.

8.4 Analysis Endpoints

Efficacy and safety endpoints that will be evaluated are listed in Section 8.4.1.

8.4.1 Efficacy/Pharmacokinetics Endpoints

8.4.1.1 Efficacy Endpoints

An initial description of efficacy measures is provided in Section 4.2.5.1.

The primary efficacy endpoint is the proportion of subjects achieving SVR₁₂.

The secondary efficacy endpoints are the following:

1. The proportion of subjects achieving SVR₂₄;
2. The proportion of subjects experiencing virologic failure (either on-treatment failure or relapse post-treatment) through FW12 among all subjects who do not discontinue study for non-treatment-related reasons.

8.4.1.2 Pharmacokinetics Endpoints

Additional details are in Section 4.2.5.3.

The primary PK endpoint for MK-3682 (and metabolites) and RZR is C_{trough}.

8.4.1.3 Exploratory Endpoints

1. The emergence of RAVs to MK-3682 or RZR when administered as part of a combination regimen.
2. The proportion of subjects with HCV RNA <LLOQ (either target detected but unquantifiable [TD(u)] or TND) at TW4, TW8, end of treatment, FW4, and FW8.
3. The collection of the viral kinetics in a subset of subjects will be used to explore the impact of early viral load decline on sustained viral response in each treatment arm.
4. The relationship between genetic variation, including but not limited to variation in IL28B, and response to the treatment administered and mechanisms of disease. Variation across the human genome will be analyzed for association with clinical data collected in this study.
5. The proportion of HIV co-infected subjects who develop HIV-1 virologic failure during protocol therapy.
6. Change from baseline in CD4+ T-cell counts in the HIV co-infected population.
7. The proportion of anti-HBc positive subjects at screening who develop HBV reactivation (see Section 7.2.3.2).

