For subjects who remain on treatment, the treatment regimen with MK-3682 + RZR for subjects with a particular GT will be extended to 16 weeks' duration and ribavirin (RBV) will be added, if the efficacy criteria for stopping enrollment/treatment allocation are met for that particular GT (see Section 5.11.4). For example, if efficacy criteria for stopping enrollment/treatment allocation are met for GT1-infected subjects at TW8, GT1-infected subjects already on treatment will receive MK-3682 + RZR for an additional 8 weeks (i.e., 16 weeks' total duration) + RBV for 8 weeks.

All subjects will be followed for 24 weeks after the end of treatment. Safety and tolerability will be carefully monitored throughout the study by the Sponsor in accordance with standard procedures.

Pharmacokinetic (PK) and Intensive Pharmacodynamic (PK/PD) Sub-studies

The purpose of the PK sub-study is to evaluate concentrations of MK-3682 and its metabolites, and RZR, as well as the PK-efficacy and PK-safety relationships. The purpose of the intensive PK/PD sub-study is to evaluate whether early viral kinetics can aid in developing a PK/PD model that can predict combinations that may be efficacious with various treatment durations.

Pharmacokinetics will be assessed in all subjects (including the first 50 and the subsequent 200), as specified in Section 4.2.5.3.

The intensive PK/PD group will only be offered to subjects once treatment allocation is opened to the subsequent 200 subjects (and will exclude the first 50 subjects). A subset of the remaining 200 subjects will participate in an intensive PK/PD group to include additional assessments for PK/PD. A total of approximately 30 subjects, (5 subjects of each GT1-6, regardless of fibrosis stage) who consent to participate, will undergo additional PD evaluations as specified in Section 4.2.5.4, and these subjects will also have additional electrocardiographs (ECGs) performed as specified in Section 7.1.2.3.

Table 1 Treatment Regimen and Subject Characteristics

Number of Subjects	Treatment Regimen	Characteristics		
		Genotype	Target Allocation	Fibrosis Stage
Total n=250	MK-3682 450 mg + RZR 180 mg for 12 weeks	GT1a	n = 35	F0-F4 (target 25-30% cirrhotic)
		GT1b	n = 15	
		GT2	n = 50	
		GT3	n = 50	
		GT4	n = 50	
		GT5	n = 25	F0-F4
		GT6	n = 25	

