- 4 A comprehensive PE will be done at screening. For all other visits, a focused PE will be conducted when clinically indicated.
- 5 Additional ECGs will be collected on subjects in the Intensive PK/PD group at Day 3 and Day 7.
- 6 This procedure only applies to female subjects of child bearing potential whose treatment regimen is modified to include RBV.
- 7 This procedure is performed only when the visit occurs prior to FW4. For female subjects of child bearing potential whose treatment regimen is modified to include RBV, urine pregnancy test and birth control confirmation should be performed when the visit occurs anytime through FW24.
- 8 All AEs that occur after the consent form is signed but before treatment allocation must be reported by the investigator if they cause the subject to be excluded from the trial, or are the result of a protocol-specified intervention, including but not limited to washout or discontinuation of usual therapy, diet, placebo treatment, or a procedure. From the time of treatment allocation through 14 days following cessation of treatment, all AEs must be reported by the investigator. The reporting timeframe for AEs meeting any serious criteria is described in Section 7.2.3.1.
- 9 For subjects whose treatment regimen is modified to include RBV, when study visits are spaced more than 1 month apart in the follow-up period, urine pregnancy test kits will be dispensed to female subjects of childbearing potential so that monthly pregnancy testing can continue for 6 months after dosing (or longer if dictated by local regulations). The test results must be provided to the investigator and/or site personnel. Subjects should be instructed to contact the investigator and/or site personnel immediately if the result of the self-pregnancy test is positive. A serum pregnancy test will be performed whenever a urine pregnancy test yields a positive result.
- 10 HBsAg, anti-HBc, and anti-HBs will be assessed at screening in all subjects. For all anti-HBc positive subjects, HBV DNA will also be assessed at screening, and both HBV DNA and HBsAg will be monitored during the trial.
- 11 PK samples will be collected as described in Section 7.1.3.2. Only subjects in the Intensive PK/PD group will have PK samples collected on Day 3, and post dose on Day 7. These subjects will also have additional HCV RNA samples collected postdose on Day 1-2, Day 3, and Day 5.

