7.1.3.2.2 Pharmacodynamics: Viral Kinetics

HCV RNA samples also will be collected at the Week 1, 2, 4, 6, 8, 10 and 12 visits for all subjects during treatment (and Week 14 and 16 visits for subjects whose treatment duration may be extended). Additional samples for HCV RNA will be collected on a subset of subjects in the Intensive PK/PD group (see [Table 13](#)). The data from this sub-study will be used to validate the existing viral dynamics model for MK-3682 and RZR. A total of approximately 30 subjects, the first 5 subjects for each GT1-6 who consent to participate, will undergo additional PK and PD evaluations and have electrocardiographs (ECGs) performed.

See Section 6.0 Trial Flow Chart and [Table 13](#) for detailed information on sample collection and visits.

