8.9 Sample Size and Power Calculations

8.9.1 Efficacy Analysis

Approximately 250 subjects will be allocated to treatment with a target allocation of 35 GT1a-, 15 GT1b-, 50 GT2-, 50 GT3-, 50 GT4-, 25 GT5-, and 25 GT6-infected subjects. These sample sizes were chosen to provide sufficient confidence of the estimated treatment response rate for the most prevalent GTs (Section 4.2.3)

Table 18 below shows the 2-sided 95% CIs for SVR_{12} under varying assumptions of the number of successes in the FAS population for each GT. Note that these intervals are not symmetric around the point estimate.

Table 18 Two-Sided 95% Confidence Intervals for SVR12 (FAS Population)

Number of subjects in FAS population	Observed Number of Successes (%)	Two-Sided 95% Confidence Interval ¹
15	15 (100.0%)	(78.2, 100.0)
	14 (93.3%)	(68.1, 99.8)
	13 (86.7%)	(59.5, 98.3)
	12 (80.0%)	(51.9, 95.7)
25	25 (100.0%)	(86.3, 100.0)
	24 (96.0%)	(79.6, 99.9)
	23 (92.0%)	(74.0, 99.0)
	22 (88.0%)	(68.8, 97.5)
35	35 (100.0%)	(90.0, 100.0)
	34 (97.1%)	(85.1, 99.9)
	33 (94.3%)	(80.8, 99.3)
	32 (91.4%)	(76.9, 98.2)
50	50 (100.0%)	(92.9, 100.0)
	49 (98.0%)	(89.4, 99.9)
	48 (96.0%)	(86.3, 99.5)
	47 (94.0%)	(83.5, 98.7)
FAS = Full Analysis Set.		
¹ Based on the Clopper-Pearson method		

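### Exploratory endpoint 3 confines the early-decline-versus-SVR question to about 30 subjects, with on average one to two failures at the SAP's illustrative rates, although early HCV RNA is collected in everyone

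*Combined protocol and SAP*

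**What the plan says.** Item 3 of Section 8.4.1.3 reads "The collection of the viral kinetics in a subset of subjects will be used to explore the impact of early viral load decline on sustained" response, and it ends by referring to each treatment arm. It names no model and does not say whether SVR12 or SVR24 is meant.

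Section 2.1 defines the subset: "A total of approximately 30 subjects, (5 subjects of each GT1-6, regardless of fibrosis stage"). It is offered only after the first cohort ("and will exclude the first 50 subjects").

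Early HCV RNA is not confined to that group. Section 7.1.3.2.2 states: "HCV RNA samples also will be collected at the Week 1, 2, 4, 6, 8, 10 and 12 visits for all subjects during treatment". The samples unique to the subset are the dense first-week ones; a footnote to the flow chart in Section 6.0 says "These subjects will also have additional HCV RNA samples collected postdose on Day 1-2, Day 3, and Day 5".

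No other listed analysis relates early decline to SVR. Item 2 of Section 8.4.1.3 reports the proportion below LLOQ at TW4 and later visits, as a response rate. The subgroup list in Section 8.10 holds baseline factors only. Section 8.6.3 leaves the detail of the exploratory analyses to a supplementary SAP.

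**The concern.** How many subjects fail, more than how densely each is sampled, limits what can be learned about early decline and SVR. The plan expects high efficacy and assigns this question to about 12% of the trial (30 of 250), so only one or two subjects who fail may be available to compare with the rest. Meanwhile Day 1, Day 7, TW2 and TW4 values exist for every subject. At stake is one exploratory question, which could be prespecified on all the available data. If it stays tied to the subset, any wider look risks being labelled post hoc.

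**Working it through.** **Inputs**
- Subset: 5 × 6 = 30, that is 5 GT1, 15 GT2–4 and 10 GT5–6 (Section 2.1).
- Whole trial (Section 8.9.1): "Approximately 250 subjects will be allocated to treatment with a target allocation of 35 GT1a-, 15 GT1b-, 50 GT2-, 50 GT3-, 50 GT4-, 25 GT5-,". GT6 makes up the remainder, with a target of 25. This gives 50 GT1, 150 GT2–4 and 50 GT5–6.
- Illustrative SVR12 rates (Section 8.1). For GT1a, "97.1% for GT1a (34 successes out of 35), the exact 95% CI is (85.1, 99.9"); for GT1b, "93.3% for GT1b (14 successes out of 15), the exact 95% CI is (68.1, 99.8"). For GT2–4, 98% or 94%. For GT5–6, 96% or 92%.

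**Plan's own figures.** Clopper-Pearson limits are the 0.025 quantile of Beta(x, n−x+1) and the 0.975 quantile of Beta(x+1, n−x). All 16 rows of Table 18 reproduce to one decimal. The documents give no precision figure for item 3.

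**Expected failures** = sum over genotype groups of n × (1 − SVR12). The GT1 rate pools 34/35 and 14/15 as 48/50, a failure rate of 0.04.
- Higher Section 8.1 rates: 5×0.04 + 15×0.02 + 10×0.04 = 0.9 in the subset; 50×0.04 + 150×0.02 + 50×0.04 = 7 in all.
- Lower Section 8.1 rates: 5×0.04 + 15×0.06 + 10×0.08 = 1.9; 50×0.04 + 150×0.06 + 50×0.08 = 15.
- Lowest rows of Table 18 (32/35, 12/15, 47/50, 22/25): 5×0.12 + 15×0.06 + 10×0.12 = 2.7; 50×0.12 + 150×0.06 + 50×0.12 = 21.

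**Distribution in the subset** (exact convolution of the 30 individual failure probabilities). For example, P(none) at the higher rates is 0.96^5 × 0.98^15 × 0.96^10 = 0.400.

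| Rates | Expected in 30 | P(none) | P(at most 1) | P(3 or more) | P(5 or more) | Expected in 250 |
|---|---|---|---|---|---|---|
| Higher, 8.1 | 0.9 | 0.400 | 0.773 | 0.060 | 0.002 | 7 |
| Lower, 8.1 | 1.9 | 0.140 | 0.425 | 0.295 | 0.038 | 15 |
| Lowest, Table 18 | 2.7 | 0.058 | 0.233 | 0.515 | 0.13 | 21 |

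Within one genotype (n = 5), the Section 8.1 rates give 0.1 to 0.4 expected failures.

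**How much information that is.** No test is planned, so Fisher's exact test serves only as a gauge. Split the 30 subjects 15/15 by early decline and put all k failures in the slow half. The two-sided p is then 2 × C(15,k)/C(30,k), capped at 1.
- k = 1: 1.0
- k = 2: 0.48
- k = 3: 0.22
- k = 4: 0.10
- k = 5: 0.042

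Five failures are needed to go below 0.05 even with perfect separation. A rank comparison is less coarse, but with one failure it describes one person: the chance that this person is the slowest of 30, with no relation present, is 1/30 = 0.033 one-sided. In all 250 subjects, 7 failures that all fall in the slow half of 125 give p = 0.014.

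**The case against.** Several points on the other side stand and limit the claim.

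- **The rates are not design assumptions.** They show interval width for hypothetical counts. Real efficacy could be lower, and Section 5.11.4 provides for that. A reader might infer that the subset cannot hold more than two failures, because the expected counts are below two. That does not follow: with a flat SVR of 94% in 30 subjects the chance of three or more is 27%, and at 96% it is 12%.
- **The sub-study has another purpose.** Sections 2.1, 4.2.5.4 and 7.1.3.2.2 describe building or validating a PK/PD and viral-dynamics model. Such a model is fitted to each subject's repeated HCV RNA values and does not depend on the number of SVR failures. A reader might infer that the sub-study cannot meet its aim; the documents do not support that. First-week kinetics before Day 7 can be studied only in this group.
- **The supplementary SAP could widen the analysis.** Item 3 does not forbid use of the other subjects' samples, so it would be wrong to say they will go unused. But the endpoint itself names the subset.
- **The all-subject analysis has limits.** Section 8.6.1 counts missing data as failure in the primary analysis, so virologic failures would be fewer than 7 to 15 at the same rates. They would be spread over six genotypes. TW4 values may mostly be at the floor: Table 4 shows 85/92 (92%) below 15 IU/mL at TW4 on the related three-drug regimen, and the LLOQ here is 15 IU/mL. The population in Table 4 differs, so this is an indication only.
- **The reference to treatment arms is loose wording.** A reader might take it as an error in a single-regimen trial, but a 16-week regimen with RBV can arise, and Section 8.5 says displays will then follow the treatment received.

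**Conclusion.** The point holds in a limited form. As written, item 3 assigns the relation between early decline and SVR to about 30 subjects, who would hold on average 0.9 to 1.9 failures at the Section 8.1 rates and 2.7 at the lowest Table 18 rows. That makes the association nearly uninformative in the subset, though not undefined. The same question could be put to all treated subjects with 7 to 15 expected failures, about eight times as many (7/0.9 = 7.8; 15/1.9 = 7.9). The result would still be modest and descriptive.

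This rests on full enrolment at the target numbers, the illustrative SVR12 rates, and subset members failing at the rate of their genotype. It is a free improvement to one exploratory item.

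**What to change.** Reword item 3 and carry the detail into the supplementary SAP:

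1. Extend the analysis to all treated subjects with the relevant samples. Relate the log10 HCV RNA change from Day 1 to Day 7 and to TW2, and the time to first value below LLOQ, to SVR12 and, separately, to virologic failure.
2. Use actual sampling times, since the flow chart allows two days either side of Day 7 and wider windows at later treatment visits.
3. Treat values below LLOQ as left-censored. Use TW4 only as below LLOQ, yes or no.
4. Adjust for genotype and baseline HCV RNA as far as the number of failures allows; otherwise present the data descriptively.
5. Keep the subset's dense Day 1 to Day 5 samples for the viral-dynamics model.
6. Replace the reference to treatment arms with presentation by regimen actually received.

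The cost is a short rewording in Section 8.4.1.3, a paragraph in the supplementary SAP and some analysis time. No sample, visit or subject is added.

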8.4.2 Safety Endpoints

An initial description of safety measures is provided in Section 4.2.5.2 and ECIs are defined in Section 7.2.3.2.

8.5 Analysis Populations

If the need arises to extend the treatment duration to 16 weeks and add RBV to the treatment regimen, data displays for both efficacy and safety will be adjusted to reflect the actual treatment received.

8.5.1 Efficacy Analysis Populations

Full Analysis Set (FAS)

The FAS population will serve as the primary population of efficacy data in this study. The FAS population consists of all subjects who are assigned to treatment and receive at least 1 dose of study treatment in this study.

Per Protocol (PP)

The PP population will serve as a supportive analysis population. The PP population excludes subjects due to important deviations from the protocol that may substantially affect the results of the primary and secondary efficacy endpoints. Non-virologic failures that are due to administrative (non-treatment-related) reasons will be excluded. Potential violations that may result in the exclusion of a subject from the PP population also include the following:

- The subject did not meet specific inclusion/exclusion criteria (for example, the subject is infected with a mixed GT infection or non-typeable GT).
- The subject received concomitant medications that are prohibited due to their potential to result in a clinically significant lowering of the MK-3682 or RZR concentrations (see Section 5.5 for specific details of prohibited medications). Further, any co-administered medication currently unidentified, but for which subsequent clinical drug-drug interaction data indicate that co-administration with MKs leads to a clinically significant lowering of MK concentrations, may also exclude a subject from the per-protocol population..
- Other violations may be identified during the course of data collection and they will be listed specifically in the CSR.

A subject with important deviations from the protocol at treatment allocation (Day 1) will be excluded from the PP population. For subjects with important deviations from the protocol as described above during the course of treatment, data obtained subsequent to the violation will be excluded from analysis.

Modified Full Analysis Set (mFAS)

The mFAS population will be used for supportive analysis of the efficacy endpoints of SVR₁₂ and SVR₂₄ and as primary analysis for the endpoint of the proportion of subjects experiencing virologic failure at FW12 as a primary analysis. The mFAS population is a subset of the FAS population, with subjects excluded for study discontinuation for reasons unrelated to the treatment regimen. Examples include loss to follow-up, discontinuation from the study due to non-drug related AEs, informed consent withdrawal, and other non-virologic failures.

The final determination on the exclusion of subjects from various analysis populations will be made prior to the final database lock and will be documented in a separate memo. Details on the approach to handling missing data are provided in Section 8.6 Statistical Methods.

